9.4.2 ANALYSIS OF THE PRIMARY EFFICACY ENDPOINT(S)

For the Primary Endpoint/Specific Aim 1, the primary analysis will be a linear random intercept model that incorporates PJ PGE₂ data from both baseline and day 28 from all randomized patients. Transformation will be used as appropriate to reduce the skewness of data and satisfy modeling assumption. The model includes randomized groups, time, and their interactions as fixed effect covariates, from which the mean change in PJ PGE₂ will be estimated for each randomized group. Effects of additional covariates, such as sex and sites, will be explored. The intra-subject correlation will be estimated from the variances of the random intercepts and residuals. Other outcome variables, such as other biomarkers and questionnaire data, can be analyzed in a similar way. The estimates about the variability of data and intrasubject correlations will be useful for designing a subsequent larger study.

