4 STUDY DESIGN

4.1 OVERALL DESIGN

This is a phase 1 / 2, randomized, placebo-controlled, double-blinded study of oral indomethacin 50 mg po BID vs. placebo po BID in patients with chronic pancreatitis. The study will be conducted at Mayo Clinic Rochester and Ohio State University.

The study **hypothesis** is:

- 1) That mean pancreatic juice PGE₂ concentration will decrease after indomethacin treatment to no more than 66% of baseline, and will be significantly lower than after placebo treatment.

[figure not shown]
Exploratory hypotheses are:

- 1) That peak blood IN levels at the conclusion of treatment will correlate with degree of change in pancreas juice (PJ) PGE₂ concentrations.
- 2) That baseline salivary and blood PGE₂ concentrations, and changes in these concentrations after treatment, will correlate with blood and saliva PJ PGE₂ concentrations.
- 3) That improvement in pain and quality of life of study participants will correlate with changes in PJ PGE₂ concentrations.

Overview: 32 participants with CP will be randomized to receive 28 days of IN 50 mg po BID or placebo (2 study arms). Blood, saliva, and pancreatic juice will be collected from each participant prior to study drug administration and again on the 28th day of study drug administration. Participants will complete daily pain diaries as well as questionnaires assessing pain and quality of life at baseline and day 28. Primary outcome is a comparison of the mean change in PJ PGE₂ concentrations at 28 days in the IN vs. placebo groups. Secondary outcomes include changes in

pain and quality of life from baseline to 28 days in the IN vs. placebo groups, and their correlation with changes in PJ PGE₂ and blood IN concentrations, as well as correlation of PJ, saliva, and blood PGE₂ concentrations (to determine whether non-invasive measures correlate with PJ measures).

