6.3 MEASURES TO MINIMIZE BIAS: RANDOMIZATION AND BLINDING

Randomization: Subjects will be assigned to receive IN or placebo according to a computer generated randomization list composed of randomized blocks of sizes of 2 or 4. Two separate sets of blocks will be created, one for subjects with alcoholic CP and the other for those with other causes of CP. Within each block, equal number of subjects will be assigned to IN and placebo. Separate sets of blocks will be provided for Mayo and Ohio State. The randomization lists will be computer generated by the study statistician ([name]), and kept in a secure computer file and paper study binder in the Mayo and Ohio State Research Pharmacies. No investigators or study personnel other than [name] and staff at Mayo/OSU research pharmacies will have knowledge of the randomization list. [name] will not participate in any aspect of subject recruitment, subject allocation, conduct of the study, or data ascertainment, but will perform data analysis with de-identified data.

Subject allocation will be known only to the staff of the Mayo and Ohio State Research Pharmacies, who will assign subjects to IN or placebo according to their randomization list provided by [name]. Allocation will be performed by matching the subject's study number with the randomization list. Allocation will not be revealed to subjects, investigators, other study personnel, or clinicians caring for subjects until all subjects have completed the clinical trial or for medical emergency. Because subjects, investigators, and study personnel will be blinded, they will not be able to determine subject allocation before or during data ascertainment.

Allocation will be performed on the day of the participant's baseline endoscopy with pancreas juice collection. One container of study medication containing 28 days of medication (56 capsules) will be dispensed to the participant that day.

In case a subject is allocated to receive study medication, but is withdrawn from the study before completing the protocol, study medication will be returned to the Research Pharmacy for disposal.

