9 STATISTICAL CONSIDERATIONS

9.1 STATISTICAL HYPOTHESES

Primary Endpoint:

- Decrease in mean pancreatic juice PGE₂ concentration after indomethacin treatment, to no more than 66% of baseline, and statistically significant in comparison to placebo.

Secondary Efficacy Endpoints:

- Changes in salivary and blood PGE₂ concentrations after study drug administration will have statistically significant correlation with changes in PJ PGE₂ concentrations and blood IN levels.
- Salivary and blood PGE₂ concentrations will have statistically significant correlation with PJ PGE₂ concentrations.
- Improvement in pain and quality of life of study participants will have statistically significant correlation with post-treatment changes in PJ PGE₂ concentrations.
- Exploratory analysis of molecular analytes (cytokine and microbiome) in blood and saliva will be done to measure effect of IN administration.

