9.2 SAMPLE SIZE DETERMINATION

We plan a sample size of 16 patients per treatment arm. Since this is a pilot study, this sample size is largely limited by budgetary restraint and is too small for a sequential study design. However, this sample size is adequate for studying the primary hypothesis with a two-sample two-sided t-test on the mean PGE₂ level at day 28 between the randomized groups. We expect to show that the treatment group has significantly lower mean PGE₂ than the placebo group. In our previous publication on PJ PGE₂,²⁰ we reported that median PJ PGE₂ level in 10 CP patients was 307 pg/ml with IQR of 249-362 pg/ml and standard deviation of 84 pg/ml. The boxplot of that data suggests that normality is a reasonable distributional assumption for the PGE₂ data. That study also found that mean PJ PGE₂ in a healthy control group was 104 pg/ml, about one third of the mean level of the CP group. If we conservatively assume that the control group in the proposed trial has 50% decrease in mean, with a Type I error of 0.05, the power of the t-test is 0.998. If we use an even more conservative mean for the control group, with 1/3 reduction in mean PGE₂, the power is 0.94. If we additionally assume that there is some data loss (due to consent withdrawal, dropout, or specimen mishandling) so that the sample size per treatment group is 12 instead of 16, the statistical power decreases to 0.85, but is still reasonable. Note that the large statistical power in the calculation above is a result of the relatively small standard deviation of the PGE₂ compared with our working assumption on the mean reduction. This assumption is supported by the data in Abu Dayyeh et al.²⁰ If this pilot study is successful, we will conduct a future study that focuses on patient centered outcomes; that study is expected to have a larger sample size because those outcomes are expected to be less sensitive to the treatment than biomarkers. The data from this pilot study will provide critical preliminary and feasibility data for the future investigation.

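### The stated power is for a t-test of day-28 PGE2, but the primary model names no between-arm test and reads most naturally as a change-score comparison

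*Combined protocol and SAP*

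**What the plan says.** **Model.** Section 9.4.2, repeated in section 4.1 under Statistical Analysis and Sample Size, makes the primary analysis a linear random-intercept model with baseline and day-28 values both as outcomes. "The model includes randomized groups, time, and their interactions as fixed effect covariates". The only output it names is a mean change for each arm. Baseline PGE2 is not a covariate, and the arms are not constrained to a common baseline mean. Sex and site are to be explored. On the correlation between visits: "The intra-subject correlation will be estimated from the variances of the random intercepts and residuals". No planning value is given.

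**Contrast.** Section 4.1 supports two readings. The Overview says: "Primary outcome is a comparison of the mean change in PJ" PGE2 between the arms. The hypothesis says that PGE2 in the indomethacin arm will fall to the 66% mark "and will be significantly lower than after placebo treatment", which can be read as a comparison of day-28 levels. The endpoint in section 9.1 has two parts: "to no more than 66% of baseline, and statistically significant in comparison to placebo".

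**Power.** Section 9.2, repeated in 4.1, uses a two-sided two-sample t-test on the mean PGE2 "level at day 28 between the randomized groups". It reports 0.998 for a 50% reduction and 0.94 for a one-third reduction at 16 per arm. For 12 per arm, "the statistical power decreases to 0.85, but is still reasonable".

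**The concern.** A power figure describes one test. If the primary test is the difference in mean change, its variance depends on the correlation between a patient's two PGE2 values, which the day-28 t-test does not involve. The figures in 9.2 then belong to a different analysis. Their relevance rests on a quantity that the trial itself sets out to estimate.

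Two things are at stake. First, two primary contrasts are open, and they can give different p-values from the same 32 patients; the choice should be fixed before the data are seen. Second, the one-third scenario is the protocol's own threshold for going on to longer trials, and the budget largely fixes the sample size. Efficient use of the baseline sample is therefore the cheapest available source of precision.

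**Working it through.** **Inputs (9.2 and 4.1).** Mean 307 pg/ml (the documents report this as a median; it is used here as the mean), SD 84, reduction of one third (307/3 = 102.3), 16 or 12 per arm, two-sided 0.05. The text places the reduction in the control group; the calculation is the same whichever arm has it.

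**Assumptions.** Equal SD at both visits and in both arms, complete pairs, raw scale. The correlation ρ is not given, so a range is shown.

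**1. The plan's own figures.** SE = 84·√(2/n).
- n = 16: SE = 29.70, ratio 102.3/29.70 = 3.446. Normal approximation 0.931; exact noncentral t (30 df) 0.915. Stated 0.94.
- n = 12: SE = 34.29, ratio 2.984. Normal 0.847; exact t (22 df) 0.814. Stated 0.85.

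The stated figures are close to the normal approximation and slightly above the exact t values. Section 9.2 also says that the healthy mean of 104 is about one third of the mean in patients, which implies 3 × 104 = 312. With 312 the exact values are 0.923 and 0.826.

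**2. What the model tests.** With complete pairs, the group-by-time estimate equals the difference in mean change. A mixed-model fit on simulated data gave the same estimate and SE as the change-score comparison. So SE = 84·√(4(1−ρ)/n), which equals the day-28 SE only at ρ = 0.5.

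**3. Baseline adjustment.** SE = 84·√(2(1−ρ²)/n × f), with f = 1 + 1/(2n−4) for estimating the slope: 1.0357 (n = 16, 29 df) and 1.05 (n = 12, 21 df).

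Example, n = 16, ρ = 0.3:
- Change: SE = 84·√(2.8/16) = 35.1, power 0.805.
- Adjusted: SE = 84·√(0.11375 × 1.0357) = 28.8, power 0.929.

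| ρ | Change, n=16 | Adjusted, n=16 | Change, n=12 | Adjusted, n=12 |
|---|---|---|---|---|
| 0 | 0.655 | 0.905 | 0.523 | 0.793 |
| 0.3 | 0.805 | 0.929 | 0.674 | 0.829 |
| 0.5 | 0.915 | 0.965 | 0.814 | 0.894 |
| 0.6 | 0.961 | 0.983 | 0.890 | 0.934 |
| 0.7 | 0.990 | 0.996 | 0.957 | 0.973 |

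The day-28 t-test has 0.915 and 0.814 at every ρ. The change contrast reaches 0.94 (n = 16) and 0.85 (n = 12) at ρ of about 0.55. Adding etiology and site to the adjusted model changes its power by less than one point (n = 16: 0.902, 0.926, 0.963 at ρ 0, 0.3, 0.5).

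**4. Where adjustment stops helping.** With equal SDs, the adjusted and change variances are equal at ρ = 2/f − 1: 0.931 (n = 16) or 0.905 (n = 12). Above that, the variance loss is at most f − 1, or 3.6% and 5%. If the day-28 SD is k times the baseline SD in both arms, compare 1 + k² − 2kρ (change) with k²(1−ρ²)f (adjusted). At k = 1.1 and n = 16 they are equal at ρ of about 0.79 (both 0.463). At ρ = 0.9 they are 0.230 and 0.238, a 3.5% difference. At k = 1.25 the first crossing is at about 0.65.

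**5. Log scale, same CV.** SD = √ln(1 + (84/307)²) = 0.2687 and shift = ln 1.5 = 0.4055. At ρ 0, 0.3, 0.5 the change contrast has power 0.83, 0.94, 0.985 (n = 16) and 0.70, 0.85, 0.94 (n = 12). The stated figures are met from ρ of about 0.3.

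**6. A 50% reduction, raw scale, n = 16.** The change contrast has 0.942 at ρ = 0 and 0.988 at 0.3, so little is lost.

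**The case against.** The strongest reply is that the mismatch is inferred. Section 9.4.2 names no between-arm test, and the same model can also give a day-28 contrast. If that was intended, section 9.2 describes essentially the right comparison. This stands as a limit: what the documents establish is an unnamed primary contrast, with the change reading the more natural one.

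A reader might infer that the trial is underpowered. The documents do not support that. They give no ρ; above about 0.55 on the raw scale the change contrast exceeds the stated power; the lowest figures in the table require no correlation between two samples from the same patient; and the permitted transformation could lower the required ρ to about 0.3. Section 9.2 does call normality reasonable, however, so the raw scale remains a live case.

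A reader might also infer that baseline adjustment is always better below ρ = 0.93. That needs equal SDs at both visits and 16 completers per arm, and no day-28 SD is given.

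It can further be said that this is a pilot with a size set mainly by budget, that section 4.1 concedes that significance may be missed, and that the 66% criterion needs change from baseline. All true. But section 9.2 still calls the sample adequate for the primary hypothesis, and each arm's change can be reported alongside an adjusted test.

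**Conclusion.** The point holds in a limited form. The power in 9.2 is for a day-28 t-test; the primary model, read with the Overview in 4.1, most naturally tests the difference in change; and the hypothesis leaves the other reading open. For a one-third reduction on the raw scale, with SD 84 at both visits, the stated 0.94 and 0.85 apply to the change contrast only from ρ of about 0.55. At ρ = 0.3 the shortfall is about 14 points at 16 per arm (0.94 against 0.805) and 18 points at 12 per arm (0.85 against 0.674). Of this, about 2.5 and 3.5 points arise because the stated figures exceed the exact t values (about 1.7 and 2.4 if the mean is 312).

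The planned test is valid and unbiased. Leaving etiology and site out of the interaction model is not a defect either. Baseline adjustment is clearly more precise at low to moderate ρ, and above the crossover the differences are small. The size of the gain depends on ρ, which is unknown.

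**What to change.** - In 9.4.2 and the matching text in 4.1 (hypothesis, Overview, Statistical Analysis and Sample Size), name one primary between-arm contrast: the day-28 PGE2 difference adjusted for baseline PGE2 on the same scale, by ANCOVA or a repeated-measures model with a common baseline mean.
- Include the randomization factors if desired. Section 6.3 uses separate lists by site and by etiology, "one for subjects with alcoholic CP and the other for those with other causes of CP".
- Keep each arm's change from its own baseline as a separate estimate for the 66% criterion.
- Restate the power in 9.2 and 4.1 for that analysis, with the exact t calculation, over a range of ρ at 16 and 12 per arm.

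The cost is wording, with no new samples, visits or participants. Against the plain day-28 t-test, the adjusted model with both factors uses three residual degrees of freedom (27 against 30 at 16 per arm). If ρ is near 0 it loses about 1 point of power at 16 per arm and 2.5 points at 12. It is more precise than that test once ρ exceeds about 0.19 (0.23 at 12 per arm).

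### Randomization is stratified by etiology and site, but the primary model omits etiology and only explores site; the cost is minor and conditional, and pre-specifying both is nearly free

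*Combined protocol and SAP*

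**What the plan says.** On allocation, Section 6.3 (repeated in Section 4.1) states: "Two separate sets of blocks will be created, one for subjects with alcoholic CP and the other for those with other causes of CP". It adds: "Separate sets of blocks will be provided for Mayo and Ohio State". The lists use "randomized blocks of sizes of 2 or 4", and "Within each block, equal number of subjects will be assigned to IN and placebo". Two factors at two levels give four strata, each held close to 1:1.

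On analysis, Section 9.4.2 (also repeated in Section 4.1) says "the primary analysis will be a linear random intercept model that incorporates" pancreatic juice PGE2 from baseline and day 28. Its terms are fixed: "The model includes randomized groups, time, and their interactions as fixed effect covariates". Then: "Effects of additional covariates, such as sex and sites, will be explored".

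Etiology is in no planned model of the primary outcome. Section 9.4.5 lists cause of pancreatitis as a variable on which the arms are described at baseline. Sex, which was not used in the randomization, has the same standing as site.

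The sample size rests on another test. Section 9.2 says "this sample size is adequate for studying the primary hypothesis with a two-sample two-sided t-test on the mean" PGE2 at day 28, with no baseline and no strata. No reason is given for leaving the stratification factors out.

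**The concern.** Blocking within strata forces the arms to be nearly balanced on etiology and site. Variation between strata then contributes almost nothing to the difference between the arms. If the strata are left out of the model, that variation can still sit in the error term. The standard error is then larger than the true sampling variation of the estimate, the test rejects too rarely under the null, and the interval is wider than it need be.

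This trial has 16 participants per arm and one primary comparison, on which Section 4.1 makes longer trials at this dose depend. Precision that costs nothing to obtain is worth having. Whether any is lost depends on which contrast is tested and whether the strata predict it.

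**Working it through.** **Inputs from the documents (Section 9.2).** CP reference level 307 pg/ml; SD 84 pg/ml; 16 per arm, or 12 after data loss; two-sided alpha 0.05. (Section 9.4.1 prints another threshold; 0.05 is used throughout here.) A one-third reduction is 307/3 = 102.3 pg/ml, and 102.3/84 = 1.22 SD.

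**Assumptions not in the documents.** The share of variance explained by the strata (R2), and the intra-subject correlation (rho).

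**Step 1: the plan's own power.** The noncentrality is delta / (SD × sqrt(2/n)).

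| Case | Stated | Normal approximation | Noncentral t |
|---|---|---|---|
| 50% reduction, 16 per arm | 0.998 | 0.999 | 0.999 |
| One-third reduction, 16 per arm | 0.94 | 0.931 | 0.915 |
| One-third reduction, 12 per arm | 0.85 | 0.847 | 0.814 |

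The stated figures are close to the normal approximation. They assume no gain from stratification.

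**Step 2: strata with a constant effect, group-by-time test.** With complete data at two visits, the group-by-time term is the difference between arms in mean change. A stratum effect that is equal at both visits is in both measurements and drops out on subtraction. Simulation at the one-third reduction (16 per arm, rho = 0.5, strata explaining 10% to 30% of variance at each visit) gives power of 0.91 with and without strata-by-time terms, and type I error of 0.045 to 0.049 either way.

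A mixed-model fit to one simulated data set shows the same. The group-by-time estimate is -99.49 with SE 26.03, and adding etiology and site main effects changes neither. Main effects alone therefore do nothing to this test.

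**Step 3: strata that predict the tested quantity.** With balanced strata, the arm difference has variance SD² × (1 - R2) × 2/n, while the unadjusted test uses about SD² × 2/n. Its t statistic shrinks by sqrt(1 - R2), so the critical value of 2.042 (30 df) acts like 2.042/sqrt(1 - R2) = 2.15, 2.28 and 2.44 for R2 = 0.1, 0.2 and 0.3. The two-sided tail areas are about 0.04, 0.03 and 0.02.

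A simulation (four equal strata, 1:1 within each, additive etiology and site effects, 40,000 trials per setting, effect 1.22 SD) gives:

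| R2 | Type I without / with strata (16 per arm) | Power without / with (16 per arm) | Power without / with (12 per arm) |
|---|---|---|---|
| 0 | 0.050 / 0.050 | 0.913 / 0.911 | 0.810 / 0.806 |
| 0.1 | 0.038 / 0.049 | 0.927 / 0.940 | 0.824 / 0.849 |
| 0.2 | 0.030 / 0.051 | 0.932 / 0.959 | 0.832 / 0.887 |
| 0.3 | 0.019 / 0.050 | 0.944 / 0.977 | 0.846 / 0.924 |

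As an analytic check at R2 = 0.2 and 16 per arm, the residual SD is 84 × sqrt(0.8) = 75.1 and the noncentrality is 102.3/(75.1 × sqrt(2/16)) = 3.85, which gives power 0.960.

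**Step 4: the change score at other correlations.** The SD of change is 84 × sqrt(2(1 - rho)). It equals 84 only at rho = 0.5, so the 1.22 SD of Step 3 applies to the day-28 level, or to change at rho = 0.5. If strata explain 20% of the variance of change, power without and with strata-by-time terms is:
- rho = 0.2: 0.761 and 0.825
- rho = 0.35: 0.851 and 0.904
- rho = 0.5: 0.934 and 0.960
- rho = 0.7: 0.995 and 0.998

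**The case against.** The strongest reply is that the planned model already deals with the problem. Its random intercept and group-by-time contrast remove any lasting difference in PGE2 between sites or etiologies, and nothing in the documents says that either factor predicts change. This stands for the group-by-time test. A reader might infer that leaving out the strata makes the planned test conservative in every case; Step 2 shows that it does not.

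Three other inferences are also unsupported:
- That the trial loses power it was sized to have. Section 9.2 uses an unadjusted t-test and counts on no gain from stratification.
- That exploring covariates leaves the primary result open to choice. Section 9.4.2 states the primary model's fixed effects, and the exploration is separate from them.
- That false positives are at risk. Any error here is in the conservative direction.

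It is also fair to say that the trial is a pilot, and that the per-protocol emphasis of Section 9.3 may erode the within-stratum balance that produces the conservatism.

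The reply does not dispose of the point, because the documents do not hold to the contrast in which strata cancel. Section 4.1 calls the primary outcome a comparison of mean change, while Section 9.2 powers a day-28 comparison, where constant stratum differences do enter the error. The hypothesis is also proportional, to no more than 66% of baseline. If strata differ in level, a proportional effect analyzed untransformed makes the change in treated participants differ by stratum.

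**Conclusion.** The mismatch between design and analysis is established from the text: both stratification factors are absent from the primary model, and etiology is not even named for exploration. Its consequence is conditional. It is nil for the group-by-time test if stratum effects are constant over time. If strata explain 10% to 30% of the variance of the tested quantity, true type I error falls to about 0.04 to 0.02. The power forgone at the one-third reduction is then about 1 to 3 points with 16 per arm and 3 to 8 with 12. For the change contrast at 20% explained, it ranges from under 1 point at rho = 0.7 to about 6 at rho = 0.2.

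These sizes rest on assumed values of R2 and rho and, in Step 3, on equal, complete strata. Confidence is high that the mismatch exists and moderate about its size. This is a free improvement of minor weight; it does not threaten validity.

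**What to change.** In Sections 9.4.2 and 4.1, state which contrast is the primary test, and make etiology (alcoholic/other) and site pre-specified terms of that model, in place of exploring site.
- If the two-visit random-intercept model is kept, enter each factor with its interaction with time. Main effects alone leave the test unchanged.
- If day 28 is compared with baseline as a covariate, enter each as a main effect.

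Keep sex exploratory. The change is to wording only and needs no new data. It uses 2 to 4 degrees of freedom and costs less than 1 point of power if the factors explain nothing.
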